Platelet Transfusion During Neonatal Open Heart Surgery

NCT03045068

Version Date: 03/04/2020

Title: Neurodevelopmental Outcome and Platelet Transfusion During Neonatal Open Heart Surgery

Principal Investigator:

General Pediatrics (The High Risk Clinic)-

[name] - Study Design, Patient recruitment, Data Collection, and Data Analysis

Co Investigators:

Anesthesiology-

[name] (Anesthesiology) – Study Design, Patient recruitment, Data Collection and Data Analysis

[name], Clinical RA - Study Design, Patient recruitment, Data Collection and Data Analysis General Pediatrics (The High Risk Clinic)-

[name] – Study Design, Patient recruitment, Data Collection and Data Analysis Pediatric Cardiology-

[name] – Study Design, Patient recruitment, Data Collection, and Data Analysis Pediatric Cardiac Surgery-

[name] – Study Design, Data Collection, and Data Analysis

[name], CPN – Patient Recruitment, Data Collection, and Data Analysis

Hypothesis:

Dilutional thrombocytopenia after cardiopulmonary bypass (CPB) is universal and there is a recent data supporting administration of donor apheresis platelets just prior to termination of bypass assist in early correction of coagulopathy, early hemostasis and lesser donor exposure of blood products after cardiac surgery. This administration of donor apheresis platelets just prior to termination of bypass also assist in favorable neurodevelopmental outcome.

Background:

Congenital heart disease (CHD) affects about 40,000 births per year in the United States, making it the most common type of birth defect.¹ Advancements in management, either operative or non-operative, for infants with CHD have improved early mortality in this patient population over the past 2-3 decades.² However, with improved survival the focus has turned to the neurodevelopmental outcomes of these patients. Studies have begun to elucidate evidence of neurodevelopmental delay in children with CHD, manifest as behavioral difficulties, executive function impairment, attention deficit hyperactivity disorder (ADHD), and other related symptoms.^{3, 6} In a prospective cohort study by Medoff-Cooper *et al.*, poor feeding skills and delayed growth rate were suggested as identifying factors for neurodevelopmental disability risk in infants with complex CHD who underwent cardiac intervention within 30 days of birth.⁴ As more infants with complex CHD survive early cardiac intervention, there has also been a growing interest to provide these patients with appropriate resources and/or interventions.⁵

It is known that CPB has been associated with risk for cerebral hypoxic-ischemic/reperfusion injury and embolic complications. However, there are few data to demonstrate details of the CPB and neurodevelopment in the patients with CHD. In a previous study in this institution (IRB#: HSC-MS-16-1034), an administration of donor apheresis platelets just prior to termination of bypass has demonstrated distinct advantages of earlier achievement of hemostasis, reduction in post-CPB transfusion, and improved postoperative outcome (significantly less mediastinal exploration for bleeding, duration of mechanical ventilation, and length of intensive care unit stay). The principal aim of this study is to understand whether the benefit of the timing of the platelet administration extends to the neurodevelopment outcome in the same patient population studied in the previous study.

Objectives:

Primary objectives – To evaluate any significant neurodevelopment differences between two groups: administration of donor apheresis platelets just prior to termination of bypass versus standard transfusion of platelet apheresis after modified ultrafiltration and protamine administration. A standardized assessment tools, Bayley Scales of Infant and Toddler Development 3rd edition (looking into five major

areas of development: cognitive, language (expressive/receptive), motor (gross/fine), will be used to evaluate the study populations' development at around 2 year of age.

Secondary objectives – To seek to provide improved intervention with long term improvement in quality of life for the patients.

Study Method:

Prospective cohort study comparing neurodevelopment between patients who underwent platelet apheresis transfusion prior to termination of CPB versus standard transfusion of platelet apheresis after modified ultrafiltration and protamine administration.

Study Population:

We will be including all the patients reviewed in the previous study in this institution (IRB#: HSC-MS-16-1034)

Treatment group -

Platelet Transfusion Management

- Pre-Termination of CPB- Platelet Transfusion 10ml/kg to be administered to the patient via central venous access when the patient has been rewarmed to 35*C, (the Sano or BT shunt clip is still on in children with SV physiology)
- 2. Post CPB- Platelet transfusion 10ml/kg via a central venous line is continued at a rate of 100 ml/hour till completion.

FFP and Cryoprecipitate:

- 1. 1 unit of cryoprecipitate administered during MUF and or after MUF as needed
- 2. FFP transfusion 10ml/kg during MUF and or after MUF as needed

PRBC and cell saver Transfusion:

1. Transfuse for target Hematocrit > 40 in neonates with SV physiology; Transfuse for Hematocrit> 33 for 2-Ventricle physiology

3- Factor Concentrate (Bebulin):

1. Based on clinical bleeding and achievement of hemostasis

Control Group –

Platelet Transfusion Management

- 1. Pre-Termination of CPB- No intervention
- 2. Post CPB- Platelet transfusion 20ml/kg via a central venous line is continued at a rate of 100 ml/hour till completion.
 - a. Initial transfusion to occur proximal to the hemofilter on the MUF circuit for as long as MUF lasts
 - b. Subsequent platelet transfusion continued till completion via central venous access to the patient

FFP and Cryoprecipitate:

- 1. 1 unit of cryoprecipitate administered during MUF and or after MUF as needed
- 2. FFP transfusion 10ml/kg during MUF and or after MUF as needed

PRBC and cell saver Transfusion:

- 1. Transfuse for target Hematocrit > 40 in neonates with SV physiology; Transfuse for Hematocrit> 33 for 2-Ventricle physiology
- 3 Factor Concentrate (Bebulin):

1. Based on clinical bleeding and achievement of hemostasis

Study Procedures:

Either a written informed consent or verbal informed consent over the phone will be obtained. The patients will be referred to the High Risk Clinic, where a neuropsychiatrist will be performing the Bayley Scales of Infant and Toddler Development at around 2 year old. The High Risk Clinic currently acts as a medical home for patients with chronic illness requiring multiple different specialty needs. We will be utilizing the developmental assessment aspect of the clinic.

Data and Safety Monitoring:

We do not anticipate any direct adverse events.

All data collected will be entered into a secure electronic database that will be encrypted and password protected (https://med.uth.edu/msit/secure-share/). The UT Secure-share sheet will be shared only with the co-investigators. A log-linking file will be maintained to keep patient information separate from the data collection sheet. No paper copies will be maintained.

Statistics**:

We will present data using following statistics, as appropriate and as applicable:

Mean with standard deviation/Median with interquartile range where applicable for continuous variables. Differences in continuous variables will utilize Wilcoxon sum rank test (e.g. *P*-values for age, weight and head circumference, and results of standardized assessment tool as appropriate)

Differences in categorical variables will utilize either Chi-square test or Fisher's exact test (e.g. *P*-values for gender, types of CHD, other diagnoses (e.g. genetics), types of operation/procedures, and results of standardized assessment tool as appropriate)

P-values <0.05 will be considered as statistically significant

**Statistics methods are subject to change to most appropriately present data

Ethics

IRB review will be requested by UTHealth's IRB

See above Data and Safety monitoring in regard to our plan to protect privacy of subjects Appropriate consent and documentation of informed consent will be sought

References:

- Centers of Disease Control and Prevention. Congenital Heart Defects (CHDs): Data & Statistics. Centers of Disease Control and Prevention [CDC website]. November 7, 2016. Available at: https://www.cdc.gov/ncbddd/heartdefects/data.html. Accessed March 30, 2019.

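### Nothing in the plan masks the Bayley examiner to platelet group, which leaves a risk of assessment bias in the only instrument named for the primary objective

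*Combined protocol and SAP*

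**What the plan says.** All references are to the combined protocol and SAP.

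- **Objectives.** The primary objective is "To evaluate any significant neurodevelopment differences between two groups", and one instrument is named for it: "A standardized assessment tools, Bayley Scales of Infant and Toddler Development 3rd edition".
- **Study Procedures.** Testing is done in the High Risk Clinic, and the examiner is described as follows: "where a neuropsychiatrist will be performing the Bayley Scales of Infant and Toddler Development at around 2 year old". That clinic serves as a medical home for chronically ill patients. For this study, the plan says: "We will be utilizing the developmental assessment aspect of the clinic".
- **Hypothesis and Background.** The stated expectation has a direction: "This administration of donor apheresis platelets just prior to termination of bypass also assist in favorable neurodevelopmental outcome". The principal aim is to learn "whether the benefit of the timing of the platelet administration extends to the neurodevelopment outcome".
- **Study Population.** "We will be including all the patients reviewed in the previous study in this institution". Platelet group therefore dates from neonatal surgery and was settled before any Bayley test under this plan.
- **Investigator list.** There are seven entries. The principal investigator and one co-investigator are listed under the High Risk Clinic. The principal investigator's roles are "Study Design, Patient recruitment, Data Collection, and Data Analysis", and all seven entries combine data collection with data analysis.
- **Data and Safety Monitoring.** Data go into an encrypted, password-protected database. Only the co-investigators share the sheet. A linking file holds patient information apart from it.

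No section mentions blinding, masking, concealment of group or an independent assessor.

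**The concern.** A Bayley score depends partly on how the examiner engages the child and scores responses. If the examiner knows which children received platelets before the end of bypass, and shares the expectation in the Hypothesis, scores in that group could drift upwards without any intent. Because the Bayley is the only instrument named for the primary objective, such drift would go straight into the main comparison. It would look like the effect being sought and could not be reliably separated from it afterwards. Enrolling more children would not remove it.

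Masking looks feasible here. The groups differ in the timing of platelets during a neonatal operation, which should not be visible in a child of about 2 years.

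**Working it through.** The plan states no figure to reproduce on this point, so the main check is a reading of the sections against each other.

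**1. Is the examiner masked?** Study Procedures names the examiner's discipline, the place and the age at testing, and says nothing about platelet group. No other section supplies a rule.

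**2. Do the data safeguards do the same job?** The Ethics section refers to them as the plan for protecting privacy. The linking file is described as separating patient information from the data sheet. It is not stated to separate group from scores, and the plan does not say where platelet group is held. Limited sharing of the sheet is a partial barrier: no investigator entry is described as a neuropsychiatrist, so the text does not identify the examiner as someone with access. The chart and the family remain possible routes to the group.

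**3. Could the group be known or guessed?** Group already exists in the institution's records. Background also reports that, in the earlier study, early platelets went with less mediastinal exploration for bleeding, shorter ventilation and a shorter intensive care stay. An examiner who read the early postoperative record could find hints of group there, even without the transfusion record.

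**4. Is score entry set apart?** Seven of seven entries combine data collection with data analysis, so no listed role is reserved for entering scores without the group code. The plan does not say who enters them.

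**5. What size could the bias have?** The documents give no sample size, SD, likely shift or share of children whose group would be known. Only the form can be written down. If a share *f* of treated children is scored *s* points too high, the bias in the mean difference is *f* × *s*, whatever the sample size. With an assumed *s* = 3:

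- *f* = 1: 1 × 3 = 3.0 points
- *f* = 0.5: 0.5 × 3 = 1.5 points
- *f* = 0.25: 0.25 × 3 = 0.75 points

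An illustration on assumed inputs only: normal scores with SD 15, no true effect, one score, a two-sided Wilcoxon test at 0.05, and simulation. The false-positive rate is about 5% with no shift.

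| Shift, share affected | 25 per group | 50 per group |
|---|---|---|
| 1.5 points, all | 6% | 8% |
| 3 points, all | 10% | 16% |
| 3 points, half | 6% | 8% |
| 5 points, half | 9% | 13% |
| 5 points, all | 20% | 36% |

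A normal approximation agrees. For 3 points with all affected at 50 per group, the standard error is 15 × √(2/50) = 3.0, so the shift is 1.0 standard error and Φ(−0.96) + Φ(−2.96) = 0.170. The simulated Wilcoxon value is 0.158.

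The table shows only that the result depends heavily on inputs nobody has. It covers one continuous score, while the plan names several developmental areas and also allows categorical analysis.

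**The case against.** The strongest reply is that the document is silent and contains nothing adverse. It does not say that the examiner knows the group. The sheet is limited to co-investigators, the study uses only the clinic's developmental assessment, the primary objective is worded neutrally, and a standardized test leaves less room for discretion. The bottom row of the table needs every treated child to be scored 5 points too high. With 3 points and half or fewer affected, the rate stays near 5–8%.

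Most of this stands, and it limits the point. It does not remove it. Restricted sharing and standardization reduce the risk, but neither is masking.

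Several stronger readings are tempting, and the documents do not support them:

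- *The examiner is unmasked, or is one of the investigators.* Two entries belong to the same clinic, but nothing identifies the examiner with either.
- *The linking file leaves group beside the scores.* The plan does not say so. It only fails to say the opposite.
- *Score entry is exposed to the same degree.* The role labels are generic and do not assign the task. Copying a completed score also leaves much less room for expectation than giving the test.
- *No analysis could ever help.* If knowledge of group varied between children and was recorded, results could be compared by that field, though imperfectly.

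**Conclusion.** The point holds as an unguarded risk in how the primary outcome is assessed. The omission is clear from the text; its consequence is unknown. A reader might infer that the Bayley scores are or will be biased, and nothing in the documents shows that.

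The size cannot be estimated from the documents. The bias would equal the share of children affected times the shift in score, and both are unknown. The false-positive rates above are illustrations on assumed inputs and should not be used to grade the problem.

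The case for acting is that the safeguard is inexpensive, feasible for this exposure, and cannot be supplied at the analysis stage. The examiner is the main concern and score entry is secondary. This is a change the plan should make; it is not a reason to doubt any results already obtained.

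**What to change.** Add to Study Procedures:

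1. The Bayley examiner is masked to platelet group and does not consult the operative, transfusion or early postoperative record before scoring. The last is included because exploration for bleeding, ventilation time and intensive care stay could hint at group.
2. Where possible, scores are entered without the group code. An existing team member who did not test the child merges the code after scores are locked.
3. For each child, record whether the group became known to the examiner.
4. For tests already done, if any (the documents do not say), report with the results whether the examiner knew the group.

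**Cost.** A few sentences, a small split of existing duties and one extra field. The examiner can stay the same, and no visits are added. Masking may be imperfect, because the chart or the family may reveal the group. Answers about past tests would rest on recall.

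### Bayley results are compared only by unadjusted tests with no between-group estimate or interval, and the assignment of platelet timing is not stated, so measured case-mix could create or hide a difference

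*Combined protocol and SAP*

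**What the plan says.** The Study Method section describes the design as "Prospective cohort study comparing neurodevelopment between patients who underwent platelet apheresis transfusion prior to termination of CPB" against the standard timing. The Study Population section takes its patients from earlier work: "We will be including all the patients reviewed in the previous study in this institution". It sets out a transfusion regimen for each group, labelled treatment and control, but no rule for who received which. No other section gives one.

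The Statistics section plans "Mean with standard deviation/Median with interquartile range where applicable for continuous variables" as summaries. For testing it says "Differences in continuous variables will utilize Wilcoxon sum rank test", with chi-square or Fisher's exact tests for categorical variables. Results of the assessment tool are given as an example under both kinds of test. The criterion is "P-values <0.05 will be considered as statistically significant". Case-mix variables appear in the categorical list ("gender, types of CHD, other diagnoses (e.g. genetics), types of operation/procedures"), for P-values of their own. A footnote adds: "Statistics methods are subject to change to most appropriately present data".

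The outcome comes from a neuropsychiatrist "performing the Bayley Scales of Infant and Toddler Development at around 2 year old". The Objectives section names five areas: cognitive, expressive and receptive language, and gross and fine motor.

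**The concern.** The Hypothesis and Background sections ask a causal question: whether earlier platelets help neurodevelopment. The planned comparison answers it only if the children tested in the two groups are alike apart from timing. The document does not say whether timing was randomised. The children analysed will also be those who survived, whose families consented and who attended at about 2 years. Testing CHD type, genetic diagnosis, operation type and sex between groups displays an imbalance but does not take it out of the Bayley comparison.

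A second gap does not depend on assignment. A P-value gives no size for the difference, and a non-significant one does not show how large a difference remains possible. Group means or medians let a reader form a crude difference, but no interval is planned for it.

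**Working it through.** **1. Text check.** The document states no sample size, SD, effect size or power, so there is no planned figure to reproduce. Reading every section for three items gives:
- assignment rule: none;
- regression, stratification, matching or weighting: none;
- between-group difference or confidence interval: none.

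**2. Inputs for an illustration.** From the document: the Wilcoxon test and the 0.05 criterion (taken as two-sided). Everything else is assumed: 25 or 50 children per group, residual SD 15, no true timing effect, and one binary prognostic factor worth 10 or 15 points (10/15 = 0.67 SD to 15/15 = 1.0 SD). The rates depend only on that ratio, so they hold on any score scale.

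**3. Spurious difference** = factor effect × difference in prevalence.
- 45/55: 10 × 0.10 = 1.0 to 15 × 0.10 = 1.5 points.
- 40/60: 10 × 0.20 = 2.0 to 15 × 0.20 = 3.0 points.
- 35/65: 10 × 0.30 = 3.0 to 15 × 0.30 = 4.5 points.

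**4. Wilcoxon false-positive rate**, 20,000 simulated trials per cell. Ranges cover both factor effects, with and without continuity correction. *Expected* means that each child's factor is drawn at random from the stated prevalence. *Realised* means that the counts are fixed, as a baseline table would show them.

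| Split | 25 per group | 50 per group |
|---|---|---|
| Expected, balanced | about 5% | about 5% |
| Expected 45/55 | 5.2%–5.9% | 6.1%–7.4% |
| Expected 40/60 to 35/65 | 6.7%–15.8% | 9.3%–27.1% |
| Realised, balanced | about 3%–4% | about 3%–4% |
| Realised 45/55 | about 4%–5% | about 5%–6% |
| Realised 35/65 | 8.0%–11.1% | 12.7%–21.0% |

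Realised 35/65 is rounded to whole children: 9 v 16 of 25, and 18 v 32 of 50. A linear model with the factor included gives 4.8% to 5.2% at expected 40/60 to 35/65. If 15 is the total rather than the residual SD, the expected 40/60 to 35/65 rates become 7.0% to 18.3% at 25 and 10.2% to 32.5% at 50.

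**5. Randomised timing with unequal attendance.** Suppose half of each group has single-ventricle physiology, and in one group 90% of those children attend against 60% of the two-ventricle children. The share among attenders in that group is 0.9/(0.9 + 0.6) = 0.60, against 0.50 in the other. The bias is 0.10 × 10 to 15 = 1.0 to 1.5 points, and false positives are 5.2% to 7.0%.

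**6. What a bare P-value leaves open.** The unadjusted 95% half-width is t(0.975, 2n−2) × SD × √(2/n), with total SD 15 assumed.
- n = 25: 2.011 × 15 × √(2/25) = 8.5 points.
- n = 50: 1.984 × 15 × √(2/50) = 6.0 points.

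**The case against.** The strongest objection is that the confounding part rests on a study the reader cannot see. The regimens are protocolised, the rules for other blood products are the same in both groups, and the groups are labelled treatment and control. Nothing shows that timing followed case-mix. This stands: what the text shows is an unstated assignment and an omitted estimate, not a demonstrated bias. A reader might infer from the cohort label that timing was chosen by clinicians according to severity, or that the unadjusted test is invalid. The document supports neither.

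The larger rates in the illustration also need care. They refer to expected prevalences and a factor worth 1.0 SD, and a realised 35/65 split gives lower rates. Under randomisation with 50% prevalence, a gap of 30 percentage points or more arises by chance in only about 3% of trials at 25 per group and under 0.5% at 50.

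It can also be said that listed imbalances would be visible in the baseline comparisons and that the footnote leaves room to adjust. Both are true. But showing an imbalance does not remove it, and a general permission to change methods commits to no analysis and allows a model to be chosen after the results are known.

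Lastly, adjustment can cost precision when covariates are weak and imbalance is wide. That also stands, and it is the reason for a short list.

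**Conclusion.** The point holds in conditional form and should be fixed. It is certain that the plan has no between-group estimate, no interval, no adjusted analysis and no statement of assignment. Whether bias follows depends on how timing was assigned and on who was tested.

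Under the assumed inputs, false positives are about 7% to 16% (25 per group) or 9% to 27% (50 per group) at expected prevalences of 40/60 to 35/65. For a realised 35/65 split they are about 8% to 11% and 13% to 21%. At 45/55 the inflation is small. Adjusting for the factor gives about 5%. These figures show the mechanism and should not be read as error rates for this study, whose size, SD and imbalance are not given.

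If timing was randomised and balance held, the unadjusted test is valid, and the gain is the interval and possibly precision. Adjustment deals with measured case-mix only. Confidence is moderate.

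**What to change.** 1. State how platelet timing was assigned in the earlier study.
2. For each Bayley area, report the between-group mean difference with a 95% confidence interval, unadjusted and adjusted by linear regression. If results are categorised, add a risk difference with a 95% interval. Keep Wilcoxon as a sensitivity analysis.
3. Pre-specify covariates fixed before surgery, in order of priority: single- v two-ventricle physiology, genetic diagnosis, sex. Before data are seen, state the number of tested children below which the lowest-priority covariate is dropped. Make the adjusted result primary if timing was not randomised; if it was, report it beside the unadjusted result. Do not adjust for post-bypass events. Use age at testing only in a sensitivity analysis, since it is set after surgery.
4. Name one primary Bayley area, or state that the five are read without a multiplicity claim.
5. Tabulate the covariates by group for children tested and not tested, and state that unmeasured confounding may remain.

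The cost is wording and a little analysis; no new patients are needed. The interval may widen. In simulations with four binary covariates that explain nothing, one more than listed here, it widens by about 6% at 20 and 2% at 50 per group when balanced, and by 28% and 22% if all four are at expected prevalences of 35/65. If one of the four explains 11% to 25% of the variance and all are balanced, the change is 0% to −8% at 20 per group and −4% to −12% at 50.

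### If Bayley scores are cut into three or more ordered classes, the chi-square or Fisher test that the plan allows ignores the order and loses power for the shift it hypothesises

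*Combined protocol and SAP*

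**What the plan says.** All of this is in the Statistics section of the combined protocol and SAP unless another section is named.

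- **Categories:** "Differences in categorical variables will utilize either Chi-square test" or Fisher's exact test. The examples are gender, type of heart defect, other diagnoses, "types of operation/procedures, and results of standardized assessment tool as appropriate". The only assessment tool named anywhere is the Bayley, third edition, which the primary objective uses.
- **Continuous variables:** "Differences in continuous variables will utilize Wilcoxon sum rank test". The examples are "age, weight and head circumference, and results of standardized assessment tool as appropriate". Bayley results therefore appear under both rules.
- **Significance:** "P-values <0.05 will be considered as statistically significant", with no statement of one or two sides.
- **Flexibility:** a footnote says "Statistics methods are subject to change to most appropriately present data".

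The documents do not say whether Bayley results will be categorised, how many classes there would be, where the cuts would lie, or which form carries the conclusion. They name no ordinal method for class tables. Study Population takes in all patients of the institution's earlier study and gives no number.

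**The concern.** Gender, type of heart defect and type of operation have no natural order, and chi-square or Fisher suits them. Bayley classes do have an order. The Hypothesis section expects a favourable effect of earlier platelets, which means movement towards better classes. A nominal test on three or more classes spreads its degrees of freedom over every possible pattern and does not reward movement in one direction.

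If such a table carried the conclusion, a real benefit would be more likely to be reported as no difference. The cohort is limited to the earlier study's patients, so under this plan the lost power cannot be regained by recruiting more. The problem is also distinct from the choice between score and class: even with a class form fixed in advance, the named tests would still ignore the order.

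**Working it through.** **No figure to reproduce.** The plan states no sample size, power, effect size or SD. Only the 0.05 level comes from the documents; two-sided testing is assumed.

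**Why order is ignored.** Pearson's statistic is X² = Σ (O − E)²/E over all cells, on K − 1 degrees of freedom for two groups and K classes. Rearranging the classes rearranges the terms and leaves the sum unchanged. Fisher's exact test ranks tables by their probability given the margins, which does not depend on class order either.

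**Two classes.** The tie-corrected rank-sum z² equals X²(N − 1)/N, where N is the total number of children, so the two tests practically coincide.

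**Scenario A (all assumed).** SD 15, means 85 and 94 (a shift of 9), scores rounded to 5 points, equal groups of n. Because of the rounding, cuts at 70 and 85 act at 67.5 and 82.5.

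- Lower group: Φ(−1.167) = 0.122 and Φ(−0.167) = 0.434, giving classes 0.122 / 0.312 / 0.566.
- Higher group: Φ(−1.767) = 0.039 and Φ(−0.767) = 0.222, giving classes 0.039 / 0.183 / 0.778.
- Noncentrality per child per group: Σ (p − q)²/(p + q) = 0.0431 + 0.0337 + 0.0335 = 0.110.
- At n = 30, 40 and 50 this gives λ = 3.3, 4.4 and 5.5. On 2 degrees of freedom (critical value 5.99), chi-square power is about 35, 45 and 55%.

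Simulation (10,000 replicates) agrees with the large-sample figures and adds the rank-sum test on the same classes:

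| Classes (cuts) | n per group | Chi-square | Rank-sum, same classes | Loss (points) |
|---|---|---|---|---|
| 3 (70, 85) | 30 | 33% | 44% | 11 |
| 3 (70, 85) | 40 | 45% | 56% | 11 |
| 3 (70, 85) | 50 | 56% | 66% | 10 |
| 4 (70, 80, 90) | 30 | 33% | 50% | 17 |
| 4 (70, 80, 90) | 40 | 45% | 63% | 18 |
| 4 (70, 80, 90) | 50 | 55% | 73% | 18 |

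With no true difference, both tests rejected in about 4.5 to 5.4% of replicates, so the gain is not bought with false positives. Rank-sum on the uncut scores (3,000 replicates) had 60, 73 and 83% power at the same sizes.

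**Scenario B (different assumptions).** Control mean 90, SD 15, shift 0.5 SD, 20,000 replicates, chi-square against rank-sum on the same classes:

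| n per group | 2 classes | 3 classes | 4 classes | 7 classes | Uncut scores, rank-sum |
|---|---|---|---|---|---|
| 30 | 30 vs 30% | 22 vs 31% | 21 vs 36% | 16 vs 43% | 46% |
| 50 | 46 vs 46% | 37 vs 48% | 38 vs 55% | 32 vs 64% | 68% |
| 100 | 75 vs 75% | 69 vs 78% | 70 vs 84% | 68 vs 91% | 93% |

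Losses run from about 9 to 11 points (three classes), 14 to 18 (four) and 23 to 33 (seven). Two classes show none.

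**Fisher.** Its power was computed for two classes only (22% against 30% for chi-square at n = 30 in scenario B). That gap reflects its conservatism, not class order. For three or more classes the claim about Fisher rests on the ordering argument above, not on a computed figure.

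**When the rank test does worse.** Take three classes with control 25/25/50% and treated 8/42/50%: fewer children in the worst class, the top class unchanged. Chi-square power was about 42, 54 and 64% at 30, 40 and 50 per group, against 9, 11 and 13% for rank-sum.

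**The case against.** The strongest reply is that the plan already holds the better test. The rule for continuous variables lists Bayley results under Wilcoxon, and rank-sum on uncut scores (60, 73 and 83%) beats even the ordinal test on classes. Power is then lost only if a class table carries the conclusion, so the larger gap is that the primary form of the Bayley result is not fixed. This stands, and it shapes the fix. It does not remove the point, because the plan leaves the class table open and names only nominal tests for it.

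Second, a split into delayed and not delayed would be a proper use of the categorical rule. This also stands: the point is limited to three or more classes.

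Third, a reader might infer that the plan commits Bayley results to a nominal test. It does not. The wording is conditional and the methods may change, so the test is permitted, not fixed. That flexibility still names no ordinal method.

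Fourth, a reader might infer that the study is wasting data it already holds. Study Procedures describes referral and Bayley testing in the future tense, and nothing in the documents says the scores exist.

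Fifth, the ordinal test is not free. The contrived pattern above shows chi-square doing far better when the difference is not a consistent shift, and a single common odds ratio would describe such a pattern poorly. The primary objective also asks about any difference between the groups, without direction. Given the directional hypothesis, this is a small cost, but it is a real one.

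**Conclusion.** The concern holds conditionally. The plan allows its primary outcome to be tested as categories by methods that ignore order. If there are three or more classes and the effect is a consistent shift, the loss is about 10 to 18 percentage points of power at 30 to 50 per group (SD 15, 9-point shift, cuts as shown). Under scenario B it is about 9 to 18 points for three or four classes, and more for seven. With two classes there is no loss from this source. Apart from the 0.05 level, every input is assumed, so the direction is secure and the size is illustrative. The documents do not show that such a table will be made or that it would decide the conclusion. The change is worth making because it concerns the primary outcome and uses a test already in the plan.

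**What to change.** In Statistics:

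1. Remove the assessment-tool item from the chi-square/Fisher examples, so that Bayley scores are tested with the Wilcoxon rank-sum test already named.
2. Add that, where a table of three or more Bayley classes is also tested, the test is the rank-sum on class rank, or a proportional-odds model reporting the common odds ratio with its 95% interval. State the classes and cuts before the results are seen.
3. Keep chi-square or Fisher for nominal variables and for any two-class split of the Bayley score.

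This takes a sentence or two and needs no new data, visits or patients. The price is lower power for differences that are not a consistent shift. Showing the full class counts by group beside the test lets a reader see such a pattern.
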